**\*\*\* Informed Consent \*\*\***

**13. Informed Consent**

NOTE: In order to complete this protocol, you must upload either a Consent Form or an Alteration of Consent Form (i.e., Cover Letter or Verbal Script) OR (if neither of those apply to your project) you must complete the Waiver of Consent information.

In the space below, please provide consent process background information for each Consent Form(s), Alteration of Consent Form(s), or Waiver(s).

**Informed Consent**

Title	Control Consent Am 4 12May2017
Consent Information Type	Consent
Sponsor's Consent Version Number: (if any)	
Consent Form Template	X Attachment Consent_Control_Group_20170512 (2)

[Consent Form Samples](http://ricro.colostate.edu/IRB/ConsentAssentTemplates.html)

Who is obtaining consent? The person obtaining consent must be knowledgeable about the study and authorized by the PI to consent human subjects.

How is consent being obtained?

What steps are you taking to determine that potential subjects are competent to participate in the decision-making process?

Title	MMJ Consent Am 4 12May2017
Consent Information Type	Consent
Sponsor's Consent Version Number: (if any)	
Consent Form Template	X Attachment Consent_MMJ_Group_20170512 (1)

[Consent Form Samples](http://ricro.colostate.edu/IRB/ConsentAssentTemplates.html)

Who is obtaining consent? The person obtaining consent must be knowledgeable about the study and authorized by the PI to consent human subjects.

How is consent being obtained?

What steps are you taking to determine that potential subjects are competent to participate in the decision-making process?

---

**\*\*\* Assent Background \*\*\***

**14. Assent Background (Complete if applicable)**

All minors must provide an affirmative consent to participate by signing a simplified assent form, unless the Investigator(s) provides evidence to the IRB that the minor subjects are not capable of assenting because of age, maturity, psychological state, or other factors.

See sample consent/assent forms at <http://ricro.colostate.edu/IRB/ConsentAssentTemplates.html>

Provide assent process background information, in the space below, for each Assent Form, Alteration Form (i.e., Cover Letter or Verbal Script), and Waiver.

**Assent Background**

-----

**\*\*\* HIPAA \*\*\***

**15. HIPAA**

**Are you using PHI\*? (See definition below)**

Y

Colorado State University is a hybrid entity and does not have a research-related HIPAA policy. If you will be working with a HIPAA covered entity (e.g., Poudre Valley Health System), you will need to follow their HIPAA guidelines. If your project will involve a HIPAA-regulated entity, in the Attachment section (#16) please attach that entity's required HIPAA consent and/or each waiver of authorization or alteration of authorization requested (e.g., waiver of authorization for access to medical records). Include HIPAA authorization language in the consent document(s) as appropriate (e.g., when enrolling subjects).

\*Protected Health Information (PHI) is health information with one or more of the following identifiers. For more information see: <http://www.hhs.gov/ocr/hipaa/>

1. Names
2. Social Security numbers
3. Telephone numbers
4. All geographic subdivisions smaller than a State, including street address, city, county, precinct, zip code, and their equivalent geocodes, except for the initial three digits of a zip code, if, according to the current publicly available data from the Bureau of the Census: (1) The geographic unit formed by combining all zip codes with the same three initial digits contains more than 20,000 people; and (2) The initial three digits of a zip code for all such geographic units containing 20,000 or fewer people is changed to 000
5. All elements of dates (except year) for dates directly related to an individual, including birth date, admission date, discharge date, date of death; and all ages over 89 and all elements of dates (including year) indicative of such age, except that such ages and elements may be aggregated into a single category of age 90 or older
6. Fax numbers
7. Electronic mail addresses
8. Medical record numbers
9. Health plan beneficiary numbers
10. Account numbers
11. Certificate/license numbers
12. Vehicle identifiers and serial numbers, including license plate numbers
13. Device identifiers and serial numbers
14. Web Universal Resource Locations (URLs)
15. Internet Protocol (IP) address numbers
16. Biometric identifiers, including finger and voice prints
17. Full face photographic images and any comparable images; and
18. Any other unique identifying number, character, or code (note this does not mean the unique code assigned by the Investigator(s) to code the research data)

---

**\*\*\* Attachments \*\*\***

**16. Attachments**

Attach relevant documents here. These could include: Collaborating Investigator's IRB approval and approved documents; Conflict of Interest information; Debriefing Script; Grant/Sub-contract; HIPAA Authorization Form from HIPAA-covered entity; Interview/Focus Group Questions; Investigator's Brochure; Letters of Agreement/Cooperation from organizations who will help with recruitment; Methodology section of associated Thesis or Dissertation project; Questionnaires; Radiation Control Office approval material; Recruitment Material (e.g., flyers, email text, verbal scripts); Sponsor's Protocol; Surveys; Other files associated with the protocol (you can upload most standard file formats: xls, pdf, jpg, tif, etc.) Please be sure to attach all documents associated with your protocol. Failure to attach the files associated with the

protocol may result in this protocol being returned to you for completion prior to being reviewed. Students: Be sure to attach the Methods section of your thesis or dissertation proposal. If this protocol is associated with a grant proposal, please remember to attach your grant.

**To update or revise any attachments, please delete the existing attachment and upload the revised document to replace it.**

**Document Type** Recruitment Material (e.g., flyers, email text, verbal scripts)

**Attachment** Recruitment\_flyer

**Document Name** Recruitment\_flyer

**Document Type** Other Protocol Material

**Attachment** MSQOL54\_995

**Document Name** MSQOL54\_995

**Document Type** Other Protocol Material

**Attachment** MSFC\_Manual\_and\_Forms

**Document Name** MSFC\_Manual\_and\_Forms

**Document Type** Other Protocol Material

**Attachment** MMJ\_use\_log

**Document Name** MMJ\_use\_log

**Document Type** Other Protocol Material

**Attachment** FSS

**Document Name** FSS

**Document Type** Other Protocol Material

**Attachment** Beck\_Depression\_Inventory

**Document Name** Beck\_Depression\_Inventory

**Document Type** Other Protocol Material

**Attachment** Activity LOG

**Document Name** Activity LOG

**Document Type** Other Protocol Material

**Attachment** activities\_specific\_balance\_scale\_nov\_5\_2012

**Document Name** activities\_specific\_balance\_scale\_nov\_5\_2012

**Document Type** Recruitment Material (e.g., flyers, email text, verbal scripts)

**Attachment** Online\_screening

**Document Name** Online\_screening

**Document Type**  
**Attachment**  
**Document Name**

**Letters of Agreement.Cooperation**  
Letter\_Dr. [name]  
Letter\_Dr. [name]

**Document Type**  
**Attachment**  
**Document Name**

**HIPAA Authorization Form**  
HIPAA Release generic  
HIPAA Release generic

**Document Type**  
**Attachment**  
**Document Name**

**Other Protocol Material**  
MOS Pain Effects Scale (PES)  
MOS Pain Effects Scale (PES)

**Document Type**  
**Attachment**  
**Document Name**

**Other Protocol Material**  
NRS\_Spasticity\_Figure 1  
NRS\_Spasticity\_Figure 1

**Document Type**  
**Attachment**  
**Document Name**

**Letters of Agreement.Cooperation**  
Letter of Support [name], IMPACT Network  
Letter of Support [name], IMPACT Network

**Document Type**  
**Attachment**  
**Document Name**

**Letters of Agreement.Cooperation**  
IMPACT 2016 Report Public Final  
IMPACT 2016 Report Public Final

**Document Type**  
**Attachment**  
**Document Name**

**Recruitment Material (e.g., flyers, email text, verbal scripts)**  
[name]\_Recruitment\_flyer\_MMJ (2) Qaualtric web address  
[name]\_Recruitment\_flyer\_MMJ (2) Qaualtric web address

**Document Type**  
**Attachment**  
**Document Name**

**Other Protocol Material**  
Rehab Measures - Modified Clinical Test of Sensory Interaction...[3726]  
Rehab Measures - Modified Clinical Test of Sensory Interaction...[3726]

**Document Type**  
**Attachment**  
**Document Name**

**Collaborating Investigator's IRB approval and associated documents**  
[name] NTF 16.6685HH  
[name] NTF 16.6685HH

**\*\*\* Event History \*\*\***

**Event History**

Date	Status	View Attachments	Letters
05/26/2016	NEW FORM CREATED		
06/28/2016	NEW FORM SUBMITTED	Y	
07/05/2016	NEW FORM PANEL ASSIGNED		
07/14/2016	NEW FORM REVIEWER(S) ASSIGNED		
07/18/2016	NEW FORM REVIEWER(S) ASSIGNED		

08/01/2016	NEW FORM REVIEWER(S) ASSIGNED		
08/17/2016	NEW FORM MOVED		
08/17/2016	NEW FORM APPROVED	Y	Y
10/03/2016	AMENDMENT 1 FORM CREATED		
10/04/2016	AMENDMENT 1 FORM SUBMITTED	Y	
10/14/2016	AMENDMENT 1 FORM REVIEWER(S) ASSIGNED		
11/04/2016	AMENDMENT 1 FORM REVIEWER(S) ASSIGNED		
11/11/2016	AMENDMENT 1 FORM MOVED		
11/11/2016	AMENDMENT 1 FORM APPROVED	Y	Y
11/11/2016	AMENDMENT 2 FORM CREATED		
11/11/2016	AMENDMENT 2 FORM SUBMITTED	Y	
11/11/2016	AMENDMENT 2 FORM APPROVED	Y	Y
02/22/2017	AMENDMENT 3 FORM CREATED		
02/22/2017	AMENDMENT 3 FORM SUBMITTED	Y	
02/23/2017	AMENDMENT 3 FORM REVIEWER(S) ASSIGNED		
03/07/2017	AMENDMENT 3 FORM APPROVED	Y	Y
05/12/2017	AMENDMENT 4 FORM CREATED		
05/15/2017	AMENDMENT 4 FORM SUBMITTED	Y	
05/16/2017	AMENDMENT 4 FORM REVIEWER(S) ASSIGNED		
05/18/2017	AMENDMENT 4 FORM MOVED		
05/18/2017	AMENDMENT 4 FORM APPROVED	Y	Y
06/06/2017	CONTINUING REVIEW 1 FORM CREATED		
06/06/2017	CONTINUING REVIEW 1 FORM SUBMITTED	Y	
06/09/2017	CONTINUING REVIEW 1 FORM REVIEWER(S) ASSIGNED		
06/19/2017	CONTINUING REVIEW 1 FORM APPROVED	Y	Y
05/30/2018	FINAL FORM CREATED		
05/30/2018	FINAL FORM SUBMITTED	Y	
05/30/2018	FINAL FORM APPROVED	Y	N
05/30/2018	CLOSED		

### *Statistical Analysis*

All data are reported as Mean (Standard Deviation) unless otherwise noted. Pearson's correlations were calculated between demographic variables (age, height, weight, BMI, disease duration) and whole brain SUV to identify possible covariates for the SPM analysis. Significant factors were individually tested as covariates during SPM analysis.

Demographic, clinical, and extracted regional SUV variables were compared between the two groups using unpaired student's t-tests. If a clinical variable differed between the two groups a Pearson's correlation was performed with it and regional SUVs. Cohen's D measures of effect size were calculated for the regional SUVs. Analysis was performed using IBM SPSS Statistics for Windows version 24 (IBM Corp., NY, USA) with alpha set to 0.05.

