We hope to determine how regular cannabis use alters resting brain activity in people with MS.

c) **Proposed Start Date (may not precede IRB approval date):**

August 2016

2.

Study Procedures (If this is a student project, the methods section of the thesis or dissertation proposal must be attached in section #16 - Attachment section.)

a) **In lay language, describe all the procedures, from screening through end-of-study, that the human subject must undergo in the research project, including study visits, drug treatments, randomization and the procedures that are part of standard of care. Please note: Do NOT respond "See Attachment Section." If you would like to add tables, charts, etc., attach those files in the Attachment section (#16).**

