Prospective participants will be recruited from the Integrative Neurophysiology Laboratory's (INPL) participant database, the clinical practice of [name], Banner Health, Greeley CO, and through advertisements in the Colorado and Wyoming Chapter of the National MS Society newsletters. All experimental procedures will be performed in the INPL (Director: [name], FACSM). Interested individuals will perform an initial screening via an online questionnaire, hosted by Qualtrics, which has a contract with the College of Health and Human Sciences. Contact information for the prospective participants' information will be accessible only to the research staff according to HIPPA regulations. After completion of the online screening form, INPL personal will contact eligible participants via phone and establish 20 case/control matched pairs, 40 total participants. After the pair has been identified INPL staff will schedule the participants' first visit. Eligibility requirements for this study are: medically diagnosed with MS, 30-75 years of age, Moderate disability (Patient Determined Disease Steps score 2-6). Cases will verbally confirm their usage of medical marijuana before matching is conducted. We will only recruit people with MS who smoke medical marijuana. Exclusion criteria include: relapse with the last 60 days; high risk for cardiovascular disease (American College of Sports Medicine risk classification); changes in disease modifying medications within the last 45 days; concurrent neurological/neuromuscular disease, concurrent conditions unrelated to MS that would exacerbate fatigue (anemia, hypothyroidism, shiftwork-related fatigue, B12 deficiency, major sleep disorder, or major depressive disorder); history of traumatic brain injury, seizure disorders, hydrocephalus, traumatic brain injury; diabetes; hospitalization within the last 90 days; alcohol dependence (>2 drinks per day); present history (last six months) of drug abuse; and inability to understand/sign informed consent. Additional participants may be screened and recruited if problems arise within a matched pair, e.g. participants drop out or are unable to meet time commitments.

Medical Marijuana users will be asked to refrain from using cannabis for 8 hours prior to all testing and training to prevent any behavioral/physiological effects of acute intoxication which result from THC.

The experimental protocol for this study consists of three testing sessions.

Session 1

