**\*\*\* Subject Population (a-g) \*\*\***

8.

Subject Population - In the space below, please detail the participants that you are requesting to recruit (include requested participant number and description of each group requested). (Input N/A if not applicable)

- a) **Requested Participant Description (Include number of participants that you plan to study and description of each group requested, if applicable).**

We plan on recruiting 40 people with MS: 20 are regular cannabis users (smokers), 20 are not users, with an estimate that approximately 5 from each group will not complete the study (i.e. drop out).

- b) **What is the rationale for studying the requested group(s) of participants?**

To investigate the effects of medical marijuana usage on physical function we will employ an observational case-control design. Cases (MS medical marijuana users) will be compared to age, sex, and disease duration matched controls (MS non-cannabis users). The research team has experience with all the methods involved.

- c) **If applicable, state the rationale for involvement of potentially vulnerable subjects to be entered into the study, including minors, pregnant women, economically and educationally disadvantaged, or decisionally impaired subjects. Specify the measures being taken to minimize the risks and the chance of harm to the potentially vulnerable subjects.**

N/A

- d) **If women, minorities, or minors are not included, a clear compelling rationale must be provided. Examples for not including minors: disease does not occur in children; drug or device would interfere with normal growth and development; etc.**

N/A

- e) **State if any of the subjects are students, employees, or laboratory personnel. They should be presented with the same written informed consent. If compensation is allowed, they should also receive it.**

N/A

- f) **Describe how potential subjects will be identified for recruitment (e.g., chart review, referral from individual's treating physician, those individuals answering an ad). How will potential participants learn about the research and how will they be recruited (e.g., flyer, email, web posting, telephone, etc.)? Attach recruitment materials in the Attachment Section (#16). Important to remember: potential subjects may not be contacted before IRB approval.**

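### The only visible analysis section rests on brain SUV, which no described session collects, and tests the motor question without a listed outcome, a primary or multiplicity control

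*Combined protocol and SAP*

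**What the plan says.** The Statistical Analysis section is the only analysis text in the visible documents, and most of it concerns SUV. Demographic variables are correlated with "whole brain SUV to identify possible covariates for the SPM analysis". Then "Demographic, clinical, and extracted regional SUV variables were compared between the two groups using unpaired student's t-tests". A follow-up step is conditional on those tests: "If a clinical variable differed between the two groups a Pearson's correlation was performed with it and regional SUVs". Effect sizes are computed for regional SUVs, and alpha is a flat 0.05. The section does not list the clinical variables, rank them or adjust for their number.

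Section 1(b) gives a brain aim in one sentence: "We hope to determine how regular cannabis use alters resting brain activity in people with MS". No procedure is attached to it. Section 2(a) says "The experimental protocol for this study consists of three testing sessions" and describes each one: questionnaires, metabolic rate, grip, activity monitoring, functional tests, balance, leg strength, walking, force steadiness and the timed-up-and-go. The visit list in section 8(m) adds no further visit. Radioisotopes are answered NO in section 4, and radiation risk is N/A in section 9(b)5.

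The title, lay summary and section 2(b) make motor function the question. The design is to "establish 20 case/control matched pairs, 40 total participants", matched on age, sex and disease duration (section 8(b)). Section 8(a) expects that "approximately 5 from each group will not complete the study".

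**The concern.** Two things do not join up.

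First, the variable at the centre of the analysis has no visible origin. A reader cannot tell under which protocol SUV was measured, in whom, or whether the brain aim is answered by this study or by another.

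Second, the question in the title has no controlled test. Several motor scores are collected, none is named for analysis, and each may be tested at 0.05. A group difference could be reported on whichever score reaches significance, and that same score then opens a further set of uncorrected correlations with regional SUVs. This matters because sections 1(b) and 10(a) look ahead to guidance on cannabis use for patients and practitioners.

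**Working it through.** **Data collected against data analysed.** I set the three session descriptions beside the Statistical Analysis section. Brain imaging appears in 0 of 3 sessions, while whole-brain or regional SUV appears in most of the analysis steps. The only link is the one-sentence aim in section 1(b).

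**No figure of the plan to reproduce.** The sample of 40 comes without an effect size, SD or power, so it cannot be re-derived. What follows shows consequences only.

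**Inputs.** Alpha is 0.05 per test (Statistical Analysis), taken as two-sided because sidedness is not stated. There are 20 per group (section 8(a)), or 15 after the expected drop-out of 5. I assume eight motor scores, counted from section 2(a): grip (Session 1); 25-foot walk, 9-hole peg, mCTSIB, knee-extensor MVC and 6-minute walk (Session 2); force steadiness and timed-up-and-go (Session 3). The correlation between scores and the correlation within matched pairs are assumptions, shown as ranges.

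**Independent scores, matching without effect.** 1 − 0.95^8 = 0.337.

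**Effect of matching on an unpaired test.** If pairs correlate at r, the true variance of the mean difference is (1 − r) times what the unpaired test assumes. With n = 20 per group the critical value 2.024 becomes 2.024/√(1 − r):
- r = 0.3: 2.420, per-test error about 0.020, and 1 − (1 − 0.0204)^8 ≈ 0.15.
- r = 0.5: 2.863, per-test error about 0.0068, and 1 − (1 − 0.0068)^8 ≈ 0.05.

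**Simulation** (20 pairs, eight equicorrelated null scores, unpaired t-test, 40,000 trials per cell). Chance of at least one p<0.05:

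| Within-pair correlation | Between-score 0 | 0.3 | 0.5 | 0.7 |
|---|---|---|---|---|
| 0 | 0.339 | 0.303 | 0.250 | 0.196 |
| 0.3 | 0.156 | 0.141 | 0.122 | 0.093 |
| 0.5 | 0.059 | 0.054 | 0.047 | 0.037 |

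The first column agrees with the hand calculation. Results for 15 pairs lie within 0.01. A paired t-test, which would use the matching, returns the rate to 0.20-0.34 at every within-pair value.

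**With one primary at 0.05 and Holm over the other seven** (unpaired, no within-pair correlation). The chance of any false claim is 0.097, 0.090, 0.079 and 0.066 at between-score correlations 0, 0.3, 0.5 and 0.7. It can exceed 0.05 because the secondary family is not gated on the primary; each part is held at 0.05.

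**Power cost.** The smallest of seven secondary p-values faces 0.05/7 = 0.0071. From the noncentral t with 80% power and no within-pair correlation, the detectable d rises from 0.91 to 1.17 at 20 per group, and from 1.06 to 1.38 at 15 per group.

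**The case against.** The strongest reply on SUV is that we do not see everything. Some pages were removed, the consent forms are not shown, and section 16 lists a collaborating investigator's IRB approval whose content is absent. That stands. The point is limited to what the visible text fails to identify.

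Two stronger readings are tempting, and the documents do not support either.
- A reader might infer from the NO and N/A radiation answers that participants had an unapproved exposure, or that the form contradicts itself. The documents do not define SUV, so a tracer is itself an inference. If imaging ran under a separate approval, those answers are correct for this form.
- A reader might infer from the continuing review, which counts six participants, all users, that no control group existed. That is an interim count from June 2017. Recruitment was continuing, 34 participants remained, and the protocol closed in May 2018. It says nothing about who was analysed.

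On the motor question, one can argue that a small observational study meant to open research avenues needs no multiplicity control. This has force and supports an exploratory label, but the analysis section does not apply one. It is also fair that the error rate depends on my choice of scores and correlations. With strong matching the unpaired test is conservative enough that the inflation disappears. The documents give no within-pair correlation, and freedom to select among unlisted scores remains whatever the rate.

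Finally, it would be wrong to say that motor outcomes have no analysis. They fall under the clinical t-tests, but are not listed or ranked.

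**Conclusion.** The point holds in a limited form. The visible text does not say where SUV came from or who was scanned, and none of the three described sessions produces it. Whether the unseen collaborating approval fills that gap cannot be judged from these documents.

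The title question is tested without a listed outcome, a primary or a multiplicity rule, and significant results trigger further uncorrected correlations. The regional-SUV group tests are equally uncorrected. The size is illustrative, not measured: about 20-34% with no within-pair correlation, 9-16% at 0.3, and 4-6% at 0.5. It rests on eight assumed scores, 20 pairs, equal correlations between scores and two-sided tests.

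This should be fixed. The motor part carries most of the weight; the SUV part alone is mainly a request to name a source.

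**What to change.** **Motor outcomes.** List the motor scores. If the data have not been examined, name one already-collected score as primary at 0.05, the choice being the sponsor's, and apply Holm to the rest. The cost is secondary power, at the size given above.

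If the data have been examined, as the past tense of the Statistical Analysis section and the closure in the Event History suggest, report every listed score instead. Label the motor comparisons, the regional-SUV group tests and the triggered correlations as exploratory, and call any choice of primary post hoc. This costs wording only.

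**SUV.** Reconcile sections 1(b) and 2(a) with the Statistical Analysis section by naming the protocol and the participants that supplied SUV. Keep conclusions from that source separate from those of the three sessions. If there is no such source, state that the brain-activity aim cannot be answered under this protocol. This too is a change of wording, with no added visits or data.

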**\*\*\* Continuing review \*\*\***

To renew your protocol: 1. Complete this one-page form; 2. If necessary, update any sections of the protocol that need to be updated for the upcoming year (e.g., change in personnel, location); 3. Electronically "sign" the application by clicking in the check box on the bottom of the "Obligations" page; 4. Remember to click "Submit Form" and confirm your intent to submit by clicking "OK" so that the IRB administrators receive your application. You must answer each question. Input N/A to answer any questions that are not applicable. NOTE: Documents that contain much of the information required to answer the participant number questions below can be found in the "Event History" section of each protocol. The status on your homepage will be "Submitted to IRB" when your submission is successful. IMPORTANT: If the Department Head has changed since your last approval, please be sure to update the Department Head listing on the personnel Information screen of your protocol.

1. Summary: Number of Participants Associated with the Protocol:

a. Total number of participants approved to date:

40 (20 MS users; 20 MS non users)

b. Number of participants studied since the last approval date:

6 (all MS users)

c. Total number of participants studied since the beginning of the project:

6

d. Number of participants remaining to study (total number of participants approved LESS the total number of participants studied to date):

34  
(14 MS users; 20 MS non users)

e. Please explain if there is a discrepancy in participant numbers (e.g., more participants responded to a survey than had been approved):

N/A

2. a. Reasons and number of withdrawals from the research (both subject and investigator initiated) since the last approval date.

2 - participants never showed up for scheduled visits and never returned communications, no procedures were performed on these participants

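### The protocol plans pairs matched on age, sex and disease duration, but outcomes are compared by unpaired t-tests without those factors, and the SAP does not say whether the analysed groups are those pairs

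*Combined protocol and SAP*

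**What the plan says.** **Design.** Section 2(a) of the protocol (Study Procedures) says that staff will "establish 20 case/control matched pairs, 40 total participants" before first visits are scheduled. Section 8(b) (Subject Population) names the factors: "Cases (MS medical marijuana users) will be compared to age, sex, and disease duration matched controls (MS non-cannabis users". Section 8(a) expects about 5 dropouts in each group. Section 2(a) allows further recruitment when a pair runs into trouble, but no analysis rule for broken pairs is given.

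**Analysis.** The Statistical Analysis section states: "Demographic, clinical, and extracted regional SUV variables were compared between the two groups using unpaired student's t-tests". It does not mention pairs or matching and gives no group sizes. Age and disease duration appear only in a screening step, which correlates "demographic variables (age, height, weight, BMI, disease duration) and whole brain SUV to identify possible covariates for the SPM analysis". It continues: "Significant factors were individually tested as covariates during SPM analysis". Sex is not on that list. A later step depends on the t-test: "If a clinical variable differed between the two groups a Pearson's correlation was performed with it and regional SUVs".

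**Who was analysed.** Section 1(b) gives the imaging aim in one sentence: "We hope to determine how regular cannabis use alters resting brain activity in people with MS". The three sessions in section 2(a) list no imaging, and the radioisotope section is marked as not applicable. At the continuing review, 6 users and no controls had been studied, and "14 MS users; 20 MS non users" remained.

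**The concern.** Matching earns its precision only if the analysis uses it, through the pair or through the matching factors. An unpaired test on matched data charges the comparison with variation that the matching has removed. If instead the analysed groups are not the pairs, this observational comparison has lost its protection against differences in age, sex and disease duration, and the t-tests do not restore it. The demographic t-tests may show an imbalance in age or duration but do not adjust for it.

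The reader cannot tell which case applies. The choice also carries forward: a clinical variable is correlated with regional SUV only if this t-test finds a difference, so the power of the test is also the chance of reaching that step.

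**Working it through.** **Inputs from the documents.** The planned size is 2 x 20 = 40. At the continuing review 40 - 6 = 34 = 14 + 20 remained, which agrees. Expected completers are 20 - 5 = 15 per group. Alpha is 0.05, taken as two-sided because the SAP does not say. No effect size, SD, power or within-pair correlation is stated, so the 40 cannot be derived from a power calculation. Everything below uses assumed ranges, with outcome SD 1 within group and power evaluated at d = 0.8.

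**Case 1: intact matched pairs.** With within-pair correlation rho, the true variance of the mean difference is 2(1 - rho)/n, but the unpaired test uses 2/n. Its standard error is therefore too large by 1/sqrt(1 - rho). Simulation with 20 intact pairs gives:

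| rho | SE ratio | Type I error, unpaired | Power, unpaired v paired |
|---|---|---|---|
| 0 | 1.00 | 5.0% | 70 v 67% |
| 0.1 | 1.05 | 3.9% | 70 v 71% |
| 0.3 | 1.20 | 2.1% | 73 v 82% |
| 0.5 | 1.41 | 0.8% | 75 v 92% |

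The error falls below 5%, so the test is conservative. With 15 intact pairs, power is 56 v 53% at rho 0 and 57 v 68% at rho 0.3.

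**Case 2: t-test against a linear model of group plus age, sex and disease duration.** The three factors jointly explain R-squared of the outcome in equal shares. Near-matched means exact on sex and close on age and duration. Unmatched means that the factors are drawn independently in each group, with no imbalance on average. Power, t-test v adjusted:

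| Sample | R-squared 0 | 0.1 | 0.2 | 0.3 |
|---|---|---|---|---|
| Near-matched, 20 per group | 69 v 68% | 70 v 74% | 71 v 78% | 72 v 84% |
| Near-matched, 15 per group, pairs broken | 56 v 54% | 56 v 59% | 57 v 64% | 57 v 70% |
| Unmatched, 20 per group | 69 v 66% | 69 v 70% | 69 v 75% | 69 v 81% |
| Unmatched, 15 per group | 56 v 51% | 56 v 55% | 56 v 60% | 56 v 66% |
| Near-matched, 10 intact pairs | 39 v 39% | 38 v 41% | 38 v 46% | 38 v 51% |
| Unmatched, 10 per group | 40 v 34% | 39 v 37% | 40 v 41% | 39 v 45% |
| Near-matched, 6 intact pairs | 24 v 22% | 24 v 24% | 22 v 26% | 21 v 29% |
| Unmatched, 6 per group | 24 v 18% | 24 v 19% | 24 v 21% | 24 v 23% |

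At 6 to 10 per group the better method depends on whether the sample is matched, so sample size alone cannot choose the model.

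**Case 3: unmatched with an imbalance (illustration only).** Suppose mean age differs by 0.5 SD and age carries one third of R-squared. The t-test bias is 0.5 x sqrt(R-squared/3): 0.09 SD at R-squared 0.1, 0.16 at 0.3 and 0.20 at 0.5. Type I error at 15 per group is then 5.8%, 6.8% and 8.4%. The adjusted model has no bias and an error of 5.0 to 5.2%. By the noncentral t distribution, the planned demographic t-test would flag that age difference 12, 19, 26 and 34% of the time at 6, 10, 15 and 20 per group. A non-significant result there is weak reassurance.

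**The case against.** The strongest reply is that the link between the pairs and the t-test is not established. The pairs were planned for a motor-function battery, while the Statistical Analysis section is a past-tense account of an SUV and SPM imaging analysis. If the imaged participants were not pairs, an unpaired test is the natural form and no pair term exists. The protocol also lists attachments that are not reproduced, including a collaborating investigator's IRB approval, which may describe that sample. This stands. It turns the first request into one for disclosure, and it leaves confounding as the live question for an unmatched sample.

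Second, the harm is of unknown size. At R-squared 0 to 0.1 and 15 to 20 per group, near-matched power changes by only -2 to +4 points. The larger gains need an R-squared that the documents do not support, and the 0.5 SD imbalance is invented for illustration. This also stands.

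Third, age and disease duration can enter the SPM analysis. That is partial cover: one factor at a time, only after a significant correlation with whole brain SUV, never sex, and not in the t-tests.

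A reader might infer more than this. One inference is that ignoring the matching inflates false positives. With positive within-pair correlation it does the opposite. Another is that the results are confounded, or that the matched design was abandoned. The documents do not show who was analysed, so neither follows.

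**Conclusion.** The mismatch between the planned matching and the written t-tests is certain, and so is the silence on pair status. The consequence is conditional:

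- **Matched, and factors predict outcome:** intervals are too wide and power is lost. At an assumed R-squared of 0.3 and d = 0.8 the loss against adjustment is about 12 points at 20 per group (72 v 84%) and 13 at 15 (57 v 70%).
- **Not matched:** the comparison is open to confounding by the three factors, in an amount the documents do not allow anyone to estimate.
- **Factors unrelated to outcome:** nothing is lost by the t-test.

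Severity is minor to moderate. Every figure rests on an assumed correlation, R-squared, effect size or imbalance, and on normally distributed outcomes.

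**What to change.** 1. State who was analysed, whether they are the matched sample, the number per group and the number of complete pairs.
2. For each clinical and regional SUV outcome, report beside the planned t-test the group difference with 95% CI from a linear model of group plus age, sex and disease duration. Keep participants whose partner dropped out. Cohen's d may stay on the raw SD.
3. Fix in advance which estimate is primary. Use the adjusted one if the analysed groups are the matched sample at about the planned 15 to 20 per group. Otherwise report both, and do not choose by achieved sample size alone. With very few unmatched participants, label the adjusted model a sensitivity analysis.

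**Cost.** This needs a few sentences in the SAP and a few lines of SPSS code, using factors the study must hold to form pairs. The model spends 3 degrees of freedom. If the factors explain nothing, power at d = 0.8 falls about 0.5 to 2 points when matched (68.8 to 68.3% at 20 per group, 24.0 to 22.1% at 6). When unmatched it falls about 3.5 to 7 points (69.1 to 65.6% at 20 per group, 24.1 to 17.5% at 6).
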